1. To determine if ACT enhances response to a high-magnitude CM procedure targeting cocaine-negative urines. It is hypothesized that initial treatment (4 weeks) with ACT and CM (ACT+CM) will produce higher response (abstinence) rates than initial treatment that combines standard Drug Counseling with CM (DC+CM).
 - 1.a. To determine if pretreatment EA level moderates the effects of ACT+CM on initial response. It is hypothesized that the benefit of ACT+CM over DC+CM on initial response (abstinence) rates will be greater in the subgroup of individuals with higher pretreatment EA scores.
 - 1.b. To determine if the effects of ACT+CM are mediated by changes in EA and reward sensitivity. It is hypothesized that ACT+CM effects on initial treatment response will be mediated by the primary hypothesized treatment mechanisms, EA and reward sensitivity.

Secondary Aims/Hypotheses:

2. To determine the best sequencing of treatment for initial non-responders. For initial non-responders, it is hypothesized that continued ACT+CM treatment with pharmacotherapy (modafinil) augmentation will be most effective in promoting abstinence relative to treatment combinations involving DC and/or placebo.
3. To determine the best sequencing of treatment for initial responders. For initial responders, it is hypothesized that continued ACT+CM will be more effective (higher abstinence rates; < 46% relapse rate) than continued DC+CM.

Study Design

Overall Research Strategy. We propose an adaptive, two-stage SMART design to test the primary research hypothesis that ACT, when used in combination with CM, will increase initial treatment response rates. Secondary hypotheses will determine the probability of benefit associated with two sequences of treatments, specifically, continued ACT+CM for initial treatment responders (dashed lines in **Figure B.3.2.i**) and continued ACT+CM with modafinil augmentation for initial treatment non-responders (double lines in **Figure B.3.2.i**).

Overview of Study Design. Note: SR=stratified randomization; R=randomization; ACT=Acceptance and Commitment Therapy; DC=Drug Counseling; CM=Contingency Management; PLA=placebo; MOD=modafinil. Abstinent=6 consecutive (2 wks) cocaine-negative (BE<150 ng/ml) urines samples.

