small treatment effect favoring augmentation with modafinil, based on our previous trials.^{29, 31, 32, 43} Among initial responders, we previously observed that approximately 54% remain abstinent (46% "relapse") over an extended period of treatment, up to 12 weeks. Using this estimate for the control group (DC+CM), we predict a difference in response rates, favoring continued ACT+CM by about 15%, translating into a relapse rate of about 30%. Importantly, these effect size estimates are derived from data in which missing data is counted as non-abstinence, which mirrors the way we will be treating missing data for our primary analyses.

Finally, given the uncertainty inherent in pre-existing empirical evidence and even greater uncertainty for conditional probabilities of response, prudence dictated that robust trial planning rely upon probability distributions of plausible effects that take into account the uncertainty of our predictions of effect, rather than simple point-estimates. Adoption of distributional specification of effect sizes and their associated uncertainty required implementation of a Bayesian statistical approach.

Data Simulation Model. Using the above outcome estimates, we conducted a Monte Carlo simulation study to determine predicted power for the planned analyses, taking into account uncertainty in parameter estimates. **Figure B.3.2.x** depicts the trial design with probability point-estimates and 95% Credible Limits for each treatment cell, derived from logistic regression models with vague neutral priors, averaged across $K = 500$ simulations. *Simulated results for anticipated cell sizes are shown in italics.* **Table B.3.2.x** displays estimates of power to detect any benefit ($H_A: \theta > 0$) conferred by the treatment hypothesized as being superior. All primary hypotheses demonstrate a > 80% chance of detecting 0.90 probability of benefit for a sample of $N = 160$. Also shown in **Table B.3.2.x** are the point-estimates and 95% Credible Intervals of specified effects averaging over the $K = 500$ simulations.

Summary. Using data-driven effect sizes that take into account uncertainty, simulation results indicate that with a sample size $N=160$, we have roughly 80% power for all primary hypotheses. Further, we stipulate *a priori* that a > 80% chance of treatment conferring benefit (i.e. $Pr(\Pr \theta > 0 | \text{data}) > 0.80$)

[figure not shown]

Table B.3.2.x.

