Effect	Posterior Probability $Pr(\theta > 0)$	Power to Detect $Pr(\theta > 0)$	Average Point Estimate	Average Interval (95% C.I.) Estimate
Effect of Initial Treatment Hypothesis Test Aim 1: Contrast 1 vs 2*	0.90	0.83	0.20	0.05-0.34
Effect of Second Treatment (Initial non-responders) Hypothesis Test Aim 2				
Contrast 5 vs 6*	0.80	0.81	0.17	0.06-0.27
Contrast 7 vs 8*	0.80	0.81	0.13	0.05-0.21
Contrast 6 vs 8*	0.85	0.80	0.16	0.07-0.25
Effect of Second Treatment (Initial responders) Hypothesis Test Aim 3:				
Contrast 3 vs 4*	0.85	0.80	0.16	0.07-0.25

*Contrast numbers correspond to numbers in black boxes on Figure B.3.2.x.

constitutes sufficient evidence for results from this Stage II project to support a “Go” decision to advance to Phase III confirmatory studies.

Protection of Human Subjects

Selection Criteria

Eligible participants will:

1. be between 18 and 60 years of age
2. meet DSM-5 criteria for current cocaine use disorder of at least moderate severity (≥ 4 symptoms)
3. have at least 1 positive urine BE specimen (≥ 150 ng/mL) during intake
4. be in acceptable health on the basis of interview, medical history and physical exam
5. agree to use an acceptable method of birth control during study participation and for one month after discontinuation of the study medication. Non-hormonal methods of contraception are recommended, including barrier contraceptives (e.g., diaphragm, cervical cap, male condom) or intrauterine device (IUD). Steroid contraceptives if used with non-hormonal methods are acceptable.
6. be able to understand the consent form and provide written informed consent
7. be able to provide the names of at least 2 persons who can generally locate their whereabouts.

Exclusion criteria include:

8. current DSM-5 diagnosis for substance use disorder (of at least moderate severity) other than cocaine, marijuana, alcohol, or nicotine
9. current alcohol use that meets for physiological dependence requiring detoxification or makes participation medically unsafe as determined by the medical director.
10. have a DSM-5 axis I psychiatric disorder or neurological disease or disorder requiring ongoing treatment and/or making study participation unsafe (e.g., psychosis, dementia).
11. significant current suicidal or homicidal ideation
12. medical conditions contraindicating modafinil pharmacotherapy (e.g., major cardiovascular disease, severe liver disease based on Child-Pugh score of B or C, serious kidney problems)

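### The claim of more than 80% power at posterior probability 0.90 for all primary hypotheses is supported by Table B.3.2.x for Hypothesis 1 only

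*Combined protocol and SAP*

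**What the plan says.** The Power paragraph announces estimates for Hypotheses 1, 2 and 3. The Data Simulation Model paragraph introduces Table B.3.2.x and then states: "All primary hypotheses demonstrate a > 80% chance of detecting 0.90 probability of benefit" for N = 160. The Summary repeats the message without a threshold: "we have roughly 80% power for all primary hypotheses". It then sets the Go criterion at a posterior probability of benefit above 0.80.

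Table B.3.2.x prints a threshold and a power for each contrast:

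| Contrast | Aim | Threshold | Power | Effect |
|---|---|---|---|---|
| 1 vs 2 | 1 | 0.90 | 0.83 | 0.20 |
| 5 vs 6 | 2 | 0.80 | 0.81 | 0.17 |
| 7 vs 8 | 2 | 0.80 | 0.81 | 0.13 |
| 6 vs 8 | 2 | 0.85 | 0.80 | 0.16 |
| 3 vs 4 | 3 | 0.85 | 0.80 | 0.16 |

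Aims and Hypotheses places Aims 2 and 3 under "Secondary Aims/Hypotheses". Items 1.a ("To determine if pretreatment EA level moderates the effects of ACT+CM on initial response") and 1.b stand under Aim 1, before that heading, and are not labelled primary or secondary. Study Design names one primary research hypothesis, in the singular: that adding ACT to CM raises initial response.

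**The concern.** The text gives one evidential standard, 0.90, for every primary hypothesis. In the table the standard falls from 0.90 to 0.85 or 0.80 for the second-stage contrasts, while power stays between 0.80 and 0.83. Three standards (0.80, 0.85, 0.90) therefore appear in one short section.

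Someone who reads only the prose would take the modafinil and relapse-prevention contrasts to be planned to the same standard as Aim 1. An inconclusive Aim 2 or Aim 3 result could then be over-read as evidence of no benefit, when the planned chance of reaching 0.90 was well below 80%. These contrasts also inform the decision on Phase III.

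**Working it through.** **1. Does the sentence match the table?** It depends on what *primary* covers.

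| Reading of *primary* | Basis in the document | Result |
|---|---|---|
| Hypothesis 1 alone | Study Design, singular wording | Matches: 0.90, power 0.83 |
| Hypotheses 1, 2 and 3 | Power paragraph; coverage of the table; plural wording | Contradicted by four of five rows |
| 1, 1.a and 1.b | Position above the secondary heading | No power figure for 1.a or 1.b |

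The second reading is the natural one, because the sentence is plural and follows directly on the introduction of a table covering Aims 1 to 3.

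**2. The Aim 1 figure.** Assume 1:1 allocation (80 per arm), fixed rates, Beta(1,1) priors and success when Pr(p1 > p0 | data) > 0.90. Exact binomial enumeration gives power 0.89 for 60% vs 40% and 0.91 for 50% vs 30%. The plan prints 0.83, but its simulation averaged over uncertainty in the effects, which lowers power. With an assumed logit SD of 0.2 per arm, Monte Carlo gives 0.82 and 0.85. So 0.83 is attainable, but it cannot be confirmed because the text does not give the distribution used.

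**3. What follows without a model.** Power cannot rise when the threshold is made stricter. The rows for 6 vs 8 and 3 vs 4 print 0.80 at threshold 0.85, so, up to rounding and simulation error (√(0.8 × 0.2 / 500) = 0.018), they cannot exceed 0.80 at 0.90. The rows for 5 vs 6 and 7 vs 8 have only 0.01 to spare when the threshold moves from 0.80 to 0.90.

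**4. Moving the table's own pairs to 0.90.** With a vague prior, a posterior threshold c acts approximately like a one-sided test at level 1 − c, so

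power at 0.90 ≈ Φ(z(c) + z(power) − z(0.90)).

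- 5 vs 6 and 7 vs 8: Φ(0.842 + 0.878 − 1.282) = Φ(0.438) = 0.67.
- 6 vs 8 and 3 vs 4: Φ(1.036 + 0.842 − 1.282) = Φ(0.597) = 0.72.
- 1 vs 2: 0.83, unchanged.

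This treats the effect as fixed. Averaging over effect uncertainty flattens the curve. If that uncertainty equalled the sampling error, the shift would shrink by √2, giving Φ(0.878 − 0.440/1.414) = 0.71 and Φ(0.842 − 0.245/1.414) = 0.75, still below 0.80.

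I did not use the interval column. For 3 vs 4 it implies a standard error of (0.25 − 0.07)/3.92 = 0.046 and a ratio of 0.16/0.046 = 3.5, which does not fit a power of only 0.80 at threshold 0.85.

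**5. Illustrative check from the stated effects.** The method is as in step 2. Figure B.3.2.x is not available, so cell sizes are assumed from the response rates: 60%/40% of 80 gives 48 and 32 responders and non-responder cells of 32/2 = 16 (ACT) and 48/2 = 24 (DC); 50%/30% gives 40 and 24 responders and cells of 20 and 28. I took 5 and 6 to be ACT cells and 7 and 8 to be DC cells. Aim 2 comparator abstinence of 10–30% is assumed. Aim 3 uses the stated 54% against 69–70%.

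| Contrast | Power at 0.90 | Power at the printed threshold | Printed power |
|---|---|---|---|
| 3 vs 4 | 0.50–0.57 | 0.61–0.66 (0.85) | 0.80 |
| 5 vs 6 | 0.39–0.54 | 0.54–0.68 (0.80) | 0.81 |
| 7 vs 8 | 0.35–0.51 | 0.55–0.67 (0.80) | 0.81 |
| 6 vs 8 | 0.40–0.59 | 0.51–0.64 (0.85) | 0.80 |

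The 3 vs 4 row uses 69% and 70% with 48/32 responders and 70% with 40/24; 69% with 40/24 gives 0.47 at 0.90 and 0.58 at 0.85. The third column shows that part of the gap to 80% is a separate problem: the rows do not reproduce at their own thresholds under these assumptions.

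**The case against.** The table prints every threshold next to its power, so nothing is hidden, and the Go rule of 0.80 is fixed in advance. No analysis, endpoint, sample size or decision rule depends on the sentence. All of this stands, and it limits the harm.

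Four stronger readings are tempting, and the documents do not support them.

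- *The claim is false however primary is read.* It is not. Study Design names a single primary research hypothesis, and for that one the sentence agrees with the table. For 1.a and 1.b a missing row leaves the claim unsupported; it does not show it to be false, and the Power paragraph never offered power for them.
- *The Summary sentence is also wrong.* It names no 0.90 threshold, and about 80% fits every row at its printed threshold. Moved to the Go threshold of 0.80 by the same shift, the table's own pairs give 0.81 or more in every row. The sentence needs its thresholds stated, but it is not untrue.
- *A second-stage result at 0.80 will be presented as meeting 0.90.* Nothing in the plan says so.
- *Power for the moderation hypothesis can be quoted.* The documents give neither an interaction effect nor an expected split of high and low EA, and urn randomization balances EA between arms without fixing that split. Any figure would be an invention.

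**Conclusion.** The concern holds in a limited form. The 0.90 claim is supported for Hypothesis 1 only. It contradicts Table B.3.2.x if Hypotheses 2 and 3 are meant, and has no support for 1.a or 1.b.

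The size of the threshold mismatch itself is best read from the table's own pairs: about 0.67 for two contrasts and 0.72 for the other two, against a claim of more than 0.80. This rests on a normal approximation with a fixed effect. The lower illustrative ranges (0.35 to 0.59 across the second-stage contrasts) rest on assumed allocation, cell sizes and Aim 2 comparator rates. They should not be read as the effect of the threshold alone.

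Confidence is high in the mismatch, which can be read off the page, and moderate in the size. This should be fixed, but the trial's conduct and conclusions do not hinge on it.

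**What to change.** - In Data Simulation Model, limit the statement about 0.90 and more than 80% to Hypothesis 1.
- State in the text that the Aim 2 and Aim 3 power figures apply at 0.80 or 0.85, row by row, and give their lower power at 0.90 from a re-run of the sponsor's own simulation.
- In the Summary, attach those thresholds to the statement of roughly 80% power.
- Use *primary* in one sense across Aims and Hypotheses, Study Design, Power, Data Simulation Model and Summary.
- Say that no power was computed for 1.a and 1.b. Do not insert an assumed figure for 1.a.
- Leave N unchanged.

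The cost is wording and one simulation re-run. The stated power for Aims 2 and 3 will look less favourable.

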Hyp. 1.a. The benefit of ACT+CM over DC+CM on initial response (abstinence) rates will be greater in the subgroup of individuals with higher pretreatment EA scores. Adding the interaction term (EA-by treatment) to the logistic regression model will evaluate the moderating effect of EA.

Hyp. 1.b. ACT+CM effects on initial treatment response will be mediated by the primary hypothesized treatment mechanisms, EA and reward sensitivity. In the context of the direct effect of treatment on response, mediational modeling will evaluate the *indirect* effect of treatment on response via EA and reward sensitivity variables, using the product moment method with bootstrapped 95% CI and Bayesian posterior distributions.

Hyp. 2. For initial non-responders, continued ACT+CM treatment with pharmacotherapy (modafinil) augmentation will be most effective in promoting abstinence relative to treatment combinations involving DC and/or placebo. Logistic regression will evaluate cocaine abstinence at the end of second treatment in a set of contrasts: (1) modafinil versus placebo within each initial treatment; (2) the sequence of ACT+CM with modafinil augmentation versus DC+CM with modafinil augmentation.

Hyp. 3. For initial responders, continued ACT+CM will be more effective (higher abstinence rates; < 46% relapse rate) than continued DC+CM. Logistic regression will evaluate cocaine abstinence/relapse at end of second treatment as a function of initial treatment (ACT+CM vs DC+CM).

Power. Power estimates for Hypotheses 1, 2 and 3 will use as the primary outcome (i.e., “response”), two consecutive weeks of cocaine abstinence (BE ≤ 150 ng/mL). Initial treatment response (abstinence) rates are expected to be $\sim 40\%$, based on our previous study¹² and pooled data across cocaine clinical trials⁸⁵; however we predict a difference in response rates, favoring ACT+CM over DC+CM by about 20%, constituting a clinically meaningful treatment effect. Among initial non responders, we expect at least a

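### The roughly 80% power given for Hyp. 2 is power for each contrast alone; joint power for the best-combination claim is about 0.70 on the printed figures

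*Combined protocol and SAP*

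**What the plan says.** In the Analysis Plan, under Hypothesis testing, Hyp. 2 states that "continued ACT+CM treatment with pharmacotherapy (modafinil) augmentation will be most effective in promoting abstinence relative to treatment combinations involving DC and/or placebo". The analysis is a logistic regression with these contrasts: "1) modafinil versus placebo within each initial treatment; (2) the sequence of ACT+CM with modafinil augmentation versus DC+CM with modafinil augmentation". No rule says how many of them must succeed.

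The Power paragraph announces estimates for Hypotheses 1, 2 and 3. Data Simulation Model then reports "All primary hypotheses demonstrate a > 80% chance of detecting 0.90 probability of benefit for a sample of $N = 160", and Summary repeats that "we have roughly 80% power for all primary hypotheses".

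The Aim 2 rows of Table B.3.2.x give, in order, the posterior threshold, power, average estimate and interval:
- "Contrast 5 vs 6* 0.80 0.81 0.17 0.06-0.27"
- "Contrast 7 vs 8* 0.80 0.81 0.13 0.05-0.21"
- "Contrast 6 vs 8* 0.85 0.80 0.16 0.07-0.25"

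A footnote says "Contrast numbers correspond to numbers in black boxes on Figure B.3.2.x". That figure is not available in the text.

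**The concern.** Hyp. 1 and Hyp. 3 have one contrast each in the table, so power per contrast and power per hypothesis are the same thing. Hyp. 2 is different. One pairwise win cannot show that a combination is the best of four. The ACT+CM with modafinil cell must at least beat the same therapy with placebo and the other therapy with modafinil. The chance that both pass cannot exceed the smaller of the two single powers and is normally below it. The plan nevertheless summarises power by hypothesis.

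The results feed a Go decision at a posterior probability above 0.80, and the plan does not say whether that applies to each contrast or jointly. A reader who trusts the 80% would underestimate how often a mixed Aim 2 result occurs when the predicted effects are real.

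**Working it through.** **Inputs from the plan.** Table B.3.2.x gives power 0.81 for 5 v 6 (threshold 0.80), 0.81 for 7 v 8 (threshold 0.80) and 0.80 for 6 v 8 (threshold 0.85).

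**Can these be reproduced?** Not exactly. The cell rates and anticipated cell sizes are in the figure that is not shown, and the distribution of effects used in the simulation is not given. The printed powers are therefore taken as correct.

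**Assumed cell numbering.** 5 = ACT+placebo, 6 = ACT+modafinil, 7 = DC+placebo, 8 = DC+modafinil. The reason is that 6 v 8 is the only non-responder row that pairs cells across the other two rows, and the only cross-therapy contrast planned for Hyp. 2 is ACT+modafinil against DC+modafinil.

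**Step 1: limits under any dependence.**
- Lower limit: 0.81 + 0.80 − 1 = 0.61.
- Upper limit: min(0.81, 0.80) = 0.80, reached only if a pass on 6 v 8 always brings a pass on 5 v 6.
- Independence, for reference: 0.81 × 0.80 = 0.648.

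**Step 2: correlation from the shared cell.** Cell 6 enters both contrasts with the same sign. With v the binomial variance and n the size of each cell,

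ρ = (v6/n6) / √[(v5/n5 + v6/n6)(v6/n6 + v8/n8)].

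Equal cells and variances give ρ = 1/√(2 × 2) = 0.50.

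**Step 3: joint power.** P(both pass) = Φ₂(z(0.81), z(0.80); ρ), with Φ₂ the bivariate normal distribution function.
- ρ = 0.50 gives 0.694. A check with 2 million random draws gives 0.694.
- Unequal cells are an assumption and are used here only to vary ρ. With 16 per ACT cell and 24 per DC cell, which is 80 per arm with 60% and 40% initial response and 1:1 re-randomization, and with equal variances, ρ = 0.548 and joint power is 0.699.
- The same cells with binomial variances at the table's effects, and DC+placebo abstinence assumed between 5% and 30%, give ρ from 0.653 down to 0.545 and joint power from 0.713 down to 0.699.

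Joint power is thus 0.69 to 0.71, or about 0.70. The chance of missing the claim when the effects are real is about 1 − 0.70 = 0.30, where the summary suggests 0.20. At the lower limit it is 1 − 0.61 = 0.39.

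**Step 4: the remaining comparison.** Being best also means beating DC+placebo. The table's effects put that gap at 0.13 + 0.16 = 0.29. Adding this comparison changes the equal-cell result only from 0.694 to 0.693.

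**The case against.** - **No all-must-pass rule is written.** The Bayesian framework section poses Aim 2 as estimation, asking for probabilities, best estimates and precision, and the Go criterion is worded for a single effect. This stands in part. No printed sum is shown to be wrong, and the joint requirement is inferred from the wording of Hyp. 2. The mismatch remains, because the plan states power by hypothesis while the table computes it by contrast.
- **Hyp. 2 is listed as secondary.** Aims and Hypotheses places it there, so the phrase about primary hypotheses might not cover it. But the Power paragraph names Hypotheses 1, 2 and 3, and the table being summarised has rows only for Aims 1, 2 and 3, with none for 1.a or 1.b.
- **The rows are already labelled as contrasts.** This is true of the table, but not of the two summary sentences.
- **The numbering could differ.** If the superior cell is always listed first, 6 v 8 would be ACT+placebo against DC+placebo. The power of ACT+modafinil against DC+modafinil would then not be printed at all, and 0.70 could not be derived. The documents cannot settle this, so 0.70 is conditional.
- **The plan simulated from distributions of plausible effects.** Correlated uncertainty in the true effects would change the joint figure. That is why the range of 0.61 to 0.80 belongs beside 0.70.

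**Conclusion.** The point holds as a misstatement of what the 80% refers to. On the printed powers, the inferred numbering and shared-cell sampling correlation, the claim that ACT+CM with modafinil is best has joint power of about 0.70. It reaches 0.80 only at the extreme of the possible dependence.

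Three stronger readings are tempting, and the documents do not support them:
- **All three contrasts must pass, giving about 0.55.** Modafinil against placebo within DC does not involve the ACT+modafinil cell, so the claim does not need it.
- **Joint power falls below one half at the cell sizes that N = 160 yields.** Those sizes are in the missing figure. Any such number rests on assumed sizes and abstinence rates.
- **The single-contrast powers are themselves wrong.** Nothing here shows that; they are taken as given.

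**What to change.** In Data Simulation Model and Summary, say that the Aim 2 figures are power per contrast, and do not extend the 80% statement to Hyp. 2 as a whole.

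Add one row to Table B.3.2.x from the existing K = 500 simulation: the proportion of trials in which ACT+CM with modafinil beats both ACT+CM with placebo and DC+CM with modafinil at the stated thresholds. That tally uses the plan's own cell sizes and effect distributions, so it replaces the 0.70 given here. Also state that if only one of the two contrasts passes, only that contrast is claimed.

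The cost is one extra count and a few changed sentences, with no added patients and no design change. The downside is that the stated power for Hyp. 2 becomes less favourable.

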Phase 1 treatments. Consenting subjects will be assigned to one of the two 4-week Phase 1 treatments, ACT+CM or DC+CM, using urn randomization to ensure balance between groups on baseline EA level, coded as "high" if AIS score > 45, or "low"≤ 45. Subjects in both treatments will be scheduled to attend three clinic visits per week (MWF) during the 4-week period. **Two** of these weekly visits will include 1-hour therapy sessions (ACT or DC).

Acceptance and Commitment Therapy-Cocaine Use (ACT). The overarching goal of ACT is to decrease experiential avoidance while increasing acceptance and willingness to experience unpleasant thoughts, feelings, and physical symptoms. More specifically, ACT will assist cocaine patients to notice their internal cravings and triggers, abandon their attempts to manage these triggers via active avoidance, suppression or other control-based strategies, and to make commitments to engage in behaviors consistent with their chosen values or goals. ACT encourages clients to experience thoughts and feelings from an observer perspective, and helps them not to believe distressing thoughts and feelings as if they are literally true and in need of action. ACT treatment will be based on the therapy manual developed and tested previously.^{38, 39} The manual covers 10 core topics listed in **Table B.3.2.vi.** Our experienced ACT therapists will be taught to use the manual as a map with flexibility to "go with the client" so long as issues of acceptance, diffusion, values, and committed action are thoroughly covered. Mindfulness exercises, metaphors, and homework sheets will be used to pursue therapeutic goals, more so than didactic instruction. Masters-level therapists with ACT experience from our previous trial ³⁸ will be trained and supervised by [name] (Co-I) and [name] (Consultant).

Drug Counseling (DC). We will use the manual-guided individual DC modeled after the NIDA Collaborative Cocaine Treatment Study ⁴⁰ and used as the active control therapy in our previous studies.^{38, 41, 42} DC approximates clinical practice as it is considered the most common type of evidence-

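### In Table B.3.2.x the Aim 2 row 6 vs 8 is identical to the Aim 3 row 3 vs 4, and its printed power of 0.80 and interval of 0.07-0.25 are not reproduced under the stated design

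*Combined protocol and SAP*

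**What the plan says.** Under Hypothesis testing, Hyp. 2 has two kinds of contrast among initial non-responders: modafinil versus placebo within each initial arm, and "the sequence of ACT+CM with modafinil augmentation versus DC+CM with modafinil augmentation".

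The Power section gives planning effects in words. Initial response is expected at about 40%, with ACT+CM ahead "favoring ACT+CM over DC+CM by about 20" percentage points. For non-responders it gives only an unquantified small effect of modafinil. For responders it takes 54% abstinent under DC+CM and a difference "favoring continued ACT+CM by about 15%, translating into a relapse rate of about 30" per cent. Data Simulation Model says the simulation used these estimates. It also says that Figure B.3.2.x shows the probability and anticipated size of each cell; that figure is not shown in this copy.

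Table B.3.2.x then prints five rows, among them "Contrast 6 vs 8" under Aim 2 and "Contrast 3 vs 4" under Aim 3:

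| Row | Threshold | Power | Estimate | 95% interval |
|---|---|---|---|---|
| 1 vs 2 (Aim 1) | 0.90 | 0.83 | 0.20 | 0.05-0.34 |
| 5 vs 6 (Aim 2) | 0.80 | 0.81 | 0.17 | 0.06-0.27 |
| 7 vs 8 (Aim 2) | 0.80 | 0.81 | 0.13 | 0.05-0.21 |
| 6 vs 8 (Aim 2) | 0.85 | 0.80 | 0.16 | 0.07-0.25 |
| 3 vs 4 (Aim 3) | 0.85 | 0.80 | 0.16 | 0.07-0.25 |

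The Summary concludes that "simulation results indicate that with a sample size $N=160$, we have roughly 80% power for all primary hypotheses" and sets a posterior probability of benefit above 0.80 as sufficient for a Go decision.

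**The concern.** The last two rows agree in every column, yet one concerns non-responders given modafinil and the other concerns responders. The design gives these contrasts different cell sizes, and there is no reason for their abstinence rates to match. All rows print power of 0.80-0.83, and the thresholds take only three values, so agreement in those two columns means little. Agreement in the estimate and in both interval limits is the telling part.

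The sequence contrast is the only planned comparison that asks whether ACT adds anything over DC in modafinil-treated non-responders. If its power is well below 0.80, a weak or null result would be misread as coming from an adequately powered comparison.

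**Working it through.** **Origin of 0.16.** In the Aim 3 input, relapse of about 30% means about 70% abstinent, and 0.70 - 0.54 = 0.16. No corresponding pair of rates for ACT+modafinil and DC+modafinil appears in the readable text.

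**Cell sizes.** N = 160. No allocation ratio is printed; assignment is made "using urn randomization to ensure balance between groups on baseline EA level". I assume 80 per arm and a 1:1 re-randomization.
- 60% v 40% initial response: non-responders 80 × 0.40 = 32 and 80 × 0.60 = 48, so modafinil cells are 16 v 24. Responders are 48 v 32.
- 50% v 30% (40% read as the overall rate): non-responders 40 and 56, so modafinil cells are 20 v 28. Responders are 40 v 24.

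The cell key is in the missing figure. I take 6 vs 8 to be the Hyp. 2 sequence contrast.

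**Method.** Power is the probability that Pr(p1 > p2 | data) exceeds the threshold, summed exactly over both binomial outcomes with the plan's Beta(1,1) priors. The half-width is 1.96 × √[p1(1-p1)/n1 + p2(1-p2)/n2].

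**Check on Aim 1** (80 v 80, threshold 0.90). At 60% v 40% the exact power is 0.89. Treating the threshold as two-sided gives about 0.82, close to the printed 0.83. The half-width is 1.96 × √[(0.24 + 0.24)/80] = 0.15, against (0.34 - 0.05)/2 = 0.145 printed. The Aim 1 interval therefore reproduces, and its power reproduces on the stricter reading. The Phase 2 results below use the more generous one-sided reading.

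**Row 6 vs 8**, difference 0.16, threshold 0.85. DC+modafinil abstinence is not given in the text, so it is shown as a range.

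| DC+mod | ACT+mod | Power, 16 v 24 | Power, 20 v 28 | Half-width, 16 v 24 | Half-width, 20 v 28 |
|---|---|---|---|---|---|
| 0.02 | 0.18 | 0.70 | 0.79 | 0.20 | 0.18 |
| 0.05 | 0.21 | 0.63 | 0.73 | 0.22 | 0.20 |
| 0.10 | 0.26 | 0.58 | 0.64 | 0.25 | 0.22 |
| 0.20 | 0.36 | 0.55 | 0.56 | 0.28 | 0.26 |
| 0.30 | 0.46 | 0.51 | 0.54 | 0.31 | 0.28 |
| 0.40 | 0.56 | 0.49 | 0.53 | 0.31 | 0.28 |
| 0.54 | 0.70 | 0.47 | 0.52 | 0.30 | 0.27 |

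One line by hand (16 v 24, 0.46 v 0.30): SE = √(0.2484/16 + 0.21/24) = 0.156. The normal approximation to power is Φ(0.16/0.156 - 1.036) ≈ 0.50, and the half-width is 1.96 × 0.156 = 0.31.

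For abstinence of 10-54% the exact range is 0.47-0.64. A simulation version reached 0.46 at its lowest, hence about 0.46-0.64. At the 0.80 threshold the range is about 0.56-0.78. With a 16:24 split and abstinence of 13-54%, power of 0.80 at the 0.85 threshold needs about 97-140 patients in the two cells together, against 40-48 available.

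**Printed interval.** The half-width is (0.25 - 0.07)/2 = 0.09, so SE = 0.09/1.96 = 0.046. That would imply power of Φ(0.16/0.046 - 1.036) ≈ 0.99, so the row's interval and its power of 0.80 disagree with each other. The interval is also narrower than Aim 1's (0.145), which uses all 160 patients.

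**Other Phase 2 rows.**
- 3 vs 4 (70% v 54%, threshold 0.85): 0.66 with 48 v 32 and 0.61 with 40 v 24, against 0.80 printed. Half-width 0.22-0.25.
- 5 vs 6 (difference 0.17, threshold 0.80, cells of 16 or 20) and 7 vs 8 (difference 0.13, cells of 24 or 28): 0.52-0.68 for placebo abstinence of 10-50%, against 0.81 printed.

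**The case against.** Three objections have force.

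First, a reader might infer that the plan has no assumption at all for this contrast. The documents do not support that. Figure B.3.2.x is described as giving a probability and size for every cell, and its absence from this copy is not a gap in the plan. What can be said is that the readable text states none.

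Second, a reader might take the power shortfall as proof that the row was copied. It is not. Row 3 vs 4, the supposed source, does not reach 0.80 either, and rows 5 vs 6 and 7 vs 8 also fall short. The evidence for copying is the identical estimate and interval together with the trace of 0.16 to Aim 3. That makes copying likely, no more.

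Third, the recalculated range is conditional. It borrows 0.16 from the row in doubt and assumes cell sizes and a baseline. Very low abstinence raises the power: at 2% it is 0.70-0.79 at the 0.85 threshold, and at the 0.80 threshold it exceeds 0.80 once abstinence is 5% or lower (0.81-0.86 at 5%). Likewise, rows 5 vs 6 and 7 vs 8 reach 0.84 with the larger cells if placebo abstinence is 2%. However, if cell 8 is DC+modafinil, as the Hyp. 2 contrast requires, the printed 0.13 for 7 vs 8 puts its abstinence at 13% or more. No abstinence rate tried brings the half-width near 0.09.

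Aims 2 and 3 are also secondary under Aims and Hypotheses, which limits the consequence.

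**Conclusion.** The concern stands in conditional form. Rows 6 vs 8 and 3 vs 4 are identical in all four columns, and the readable text gives no ACT versus DC effect for modafinil-treated non-responders. With 1:1 allocation at both steps, a 20-point difference in initial response, the printed 0.16 and DC+modafinil abstinence of at least 10%, power is about 0.46-0.64 at the row's own threshold rather than 0.80. The interval is the firmer finding: a half-width of 0.18 or more at every abstinence rate tried, against 0.09 printed.

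It would go too far to say that the printed 0.80 has been shown to belong to another contrast, or that the design fixes power at 0.46-0.64 whatever the cell rates. The shortfall also reaches the other Phase 2 rows, so correcting one row would not be enough.

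**What to change.** Check row 6 vs 8 against the simulation output and Figure B.3.2.x. State the assumed abstinence for ACT+modafinil and DC+modafinil non-responders and where each comes from. Rerun the simulation for the sequence contrast named under Hyp. 2 and print the resulting power and interval. If no effect can be justified, say that this contrast will be estimated but is not powered. Recheck and restate the power and intervals of rows 3 vs 4, 5 vs 6 and 7 vs 8 at the same time, and bring the Summary's power statement into line.

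The cost is a simulation rerun and a table and text correction, with a less favourable stated power. The sample size does not change.
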